Study Duration	
The anticipated timeline for this study is as follows:
 
 • Subject enrolment begins: Sept 2016 • Last subject visit anticipated: Jan 2017 • Visits: 
V1: Screening & optimize prescription for Avaira toric V2: Dispense new or optimized prescription Avaira Toric - this visit may not be necessary if subjects habitually wear optimized power Avaira Toric V3: Baseline Avaira Toric & Avaira Vitality Toric dispense V4: 2 week follow-up wearing Avaira Vitality Toric V5: 1 month follow-up wearing Avaira Vitality Toric & Exit

Patient Population	Habitual toric contact lens wearers that provide written informed consent and meet protocol entry criteria.
Sample Size	Target enrollment of 48 subjects with the hope of at least 44 subjects being in the analysis cohort.
Study Center Location (US)	USA
Number of Centers	Multi-Center, 4 sites.

Patient Follow-up	
Patients enrolled in this study will be followed up after the each lens dispensing session. Follow-ups at:
 
 ○ at least 1 month lens wear of Avaira Toric ○ 2-week and 1 month wear of Avaira Vitality Toric
Primary Endpoints	
 • Visual acuity with contact lenses, • Lens fit performance (centration, rotation, blink movement) • Investigator's fit acceptability
[REDACTED]	[REDACTED]

Table of Contents

1	Introduction	8
2	Study Objective	8
3	Study Hypothesis	8
3.1	Study Hypothesis.....	8
4	Study Design	9
5	Study Population	9
5.1	Sample Size Calculation.....	9
6	Investigational Sites	9
6.1	Number of Sites.....	9
6.2	Investigator Recruitment.....	9
7	Ethics Review / Statement of Compliance	10
7.1	Relevant Standards / Guidelines	10
7.2	Institutional Review Board	10
7.3	Clinical Trial Registration	10
7.4	Informed Consent.....	10
8	Potential Risks and Benefits to Human Subjects	10
9	Materials and Methods	11
9.1	Subjects.....	11
	Inclusion criteria	11
9.2	Study Materials.....	13
9.2.1	Contact lens.....	13
9.2.2	Contact Lens care.....	13
9.2.3	Rewetting/ lubricating eye drops	13
9.2.4	Storage of Study Medications/Treatments	13
9.2.5	Clinical Supply Inventory.....	14
9.2.6	Disposal of Consumables	14
9.2.7	Masking and Control of Study Materials.....	14
9.2.8	Ordering and Accountability of Study Materials.....	14
9.3	Visit Schedule and Procedures.....	14
9.3.1	Visit 1: Screening visit & Establish Optimum Prescription	15
9.3.2	Visit 2: Dispense of Avaira Toric Lens.....	18

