9.3.3	Visit 3: Baseline with Avaira Toric & Dispense of Avaira Vitality Toric lenses.....	19
9.3.4	Visit 4: 2-week follow up for Avaira Vitality Toric	21
9.3.5	Visit 5: 1-month follow up on Avaira Vitality Toric Lenses & Study Exit	22

10	Adverse Events and their Reporting	24
10.1	Adverse Response Definitions	24
10.2	Procedures for Adverse Events	26
10.3	Reporting Adverse Events	27
10.4	Discontinuation from the Study	27
11	Statistical Analysis	27
11.1	Statistical analysis	27
12	Data Quality Assurance	28
12.1	Study monitoring	28
12.2	Record keeping	28
12.3	Record retention	28
12.4	Data Entry / Data Management	28
12.5	Confidentiality	29
12.6	Publication	29
13	Study Costs and Subject Compensation	29

1 Introduction

The utilization of soft toric contact lenses has increased significantly over the past few years. CooperVision (CV) produces a number of toric contact lens products including the Avaira toric brand (Enfilcon A) and Avaira Vitality brand (Fanfilcon A). All Enfilcon A toric lenses and Fanfilcon A toric lenses feature CooperVision's exclusive Aquaform® Technology and PEG (Polyethylene Glycol). This combination of material technologies provides a contact lens with high oxygen permeability that is naturally wettable and offers unique comfortable experience.

This study is designed to evaluate how adapted contact lens wearers of Enfilcon A toric lenses will perform following a refit with Fanfilcon A toric lenses, a novel soft contact lens with optimized lens geometry and enhanced water content and UV protection, over one month of daily wear. Overall lens wear experience, including visual quality, lens fit and subjective responses will be assessed.

2 Study Objective

The aim of this study is to determine if adapted contact lens wearers of Enfilcon A toric lenses can be confidently refit into Fanfilcon A toric lenses and be successful after at least one month of daily wear.

Primary outcomes:

- High contrast distance visual acuity (Snellen) with contact lenses
- Lens fit performance (centration, corneal coverage, post blink movement)
- Investigator's fit acceptability

3 Study Hypothesis

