5.1 Sample Size Calculation

A sample size calculation was provided based on the 'subjective comfort just before lens removal' (0-10 scale) data on file at CooperVision from study EX-MKTG-63, which gave a standard deviation of 2.4. For an alpha level of 0.05 and power of 0.8, a sample size of 44 will detect a difference of 1.04, which has been confirmed as acceptable by the sponsor.

We recommend dispensing lenses to at least 48 subjects to be sure to have 44 subjects in the eligible analysis population ie. 12/13 at each of the 4 sites.

6 Investigational Sites

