9.3 Visit Schedule and Procedures

The visit schedule is shown in Table 2 below.

Table 2: Visit schedule

Visit code	Visit schedule	Visit Description
1	—	Screening and establish optimum prescription with Avaira Toric lenses.
2	1 to 2 weeks from Visit 1*	Dispense new or modified power Avaira Toric (scheduled when lenses are available)*
3	Greater than 28 days from V2 **	1-month Baseline Data collection wearing Avaira Toric AND dispense Avaira Vitality Toric**
4	2-weeks from Visit 3 (12-16 Days from V3)	2-week progress visit with Avaira Vitality Toric
5	1 month from Visit 3 (27-32 Days from V3)	1-month progress visit with Avaira Vitality Toric AND Study exit

**Note: Visit 2 is only necessary if a change in Avaira Toric power is required, or if a refit into Avaira Toric is required for adaptation*

***Note: This visit will be scheduled when Avaira Vitality Toric lenses are available to be dispensed*

The forms that need to be completed at each visit is outlined in Table below:

Table 2: Study Forms

Forms	Visit 1 / 1R	Visit 2 / 2R	Visit 3	Visit 4	Visit 5
Informed Consent Letter	X				
Inclusion/Exclusion	X				
Avaira Vitality Prescription Form	X*	X			
Avaira Toric Prescription Form	X**	X			
Biomicroscopy	X	X	X	X	X
Avaira Toric Dispense		X			
Avaira Toric Re-Dispense		X			
Baseline Avaira Toric			X		
Avaira Vitality Toric Dispense			X		
2W Avaira Vitality Toric				X	
1M Avaira Vitality Toric					X
Appendix 8 Subjective Assessment			X	X	X
Appendix 25 Subjective Assessment Insertion			X		
Appendix 9 Agreement questionnaire			X	X	X
Appendix 11 Lens Preference questionnaire				X	X
Investigator's preference			X	X	X

**Note: Avaira Vitality Prescription Form will be completed at V1 ONLY for those subjects that are current Avaira Toric wearers and do not require a change in prescription*

***Note: Contact Lens Order Form will be completed at V1 ONLY for those subjects that require fit into new or modified Avaira Toric lenses*

[figure not shown]

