11.1 Statistical analysis

Descriptive statistics will be provided on information regarding baseline variables (e.g., age, gender). Differences between lenses and over time will be compared using Paired t-tests. Paired t-tests

/analysis of variance for normal (interval/continuous) data. The appropriate test will be selected based on tests of normality. Means and standard deviations will be provided for each variable.

A Binomial test will be used to analyze the results for the count data of subjective preferences. The number of "no preference" will be evenly distributed to the two options on the basis they would be equally likely to choose either. All subjects who were evaluated will be used in the analysis. In the event of missing data, individual data points will be excluded in the analysis and not extrapolated from the collected data.

12 Data Quality Assurance

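### Section 11.1 tests evenly split no-preference answers as binomial data: p-values come out too large, power is lost when many subjects are undecided, and an odd count has no rule

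*Combined protocol and SAP*

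**What the plan says.** Section 11.1 states: "A Binomial test will be used to analyze the results for the count data of subjective preferences". Subjects without a preference are not set aside; their number "will be evenly distributed to the two options on the basis they would be equally likely to choose either". The next sentence reads "All subjects who were evaluated will be used in the analysis", so undecided subjects count as trials in the test. The section's missing-data rule concerns absent data points and says nothing about an odd number of undecided answers. No significance level or sidedness is given for this test.

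The forms table in Section 9.3 schedules the "Appendix 11 Lens Preference questionnaire" at Visits 4 and 5. The synopsis sets the likely sample size: "Target enrollment of 48 subjects with the hope of at least 44 subjects being in the analysis cohort". The primary outcomes in Section 2 are visual acuity, lens fit and investigator-rated fit acceptability. Preference is not among them. Part of the endpoint list in the synopsis is redacted, so the rank of preference is not visible.

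**The concern.** A binomial test with null proportion one half treats every counted subject as an independent fair coin toss. A subject whose answer is assigned by rule is not a coin toss. The stated rationale, that undecided subjects would choose either lens with equal chance, would justify random draws. It does not justify a fixed half-and-half split that is then counted as if it were random.

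Two things are at stake. With many undecided subjects, a real preference for or against the new lens can be missed at borderline results. With an odd count, a choice made after the data are seen can decide significance.

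**Working it through.** **Inputs.** From the documents: n = 44 (analysis target) to 48 (enrolment target), the binomial test, the even split, and all evaluated subjects counted. Assumed, because the documents do not say: two-sided 0.05 (the hypothesis in Section 3.1 is non-directional), an undecided share of 10% to 50%, and 75:25 preference among choosers.

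**The plan's own figure.** Section 5.1 sizes the study on comfort, not preference. A two-sided paired t-test with 2.4 as the SD of the differences and n = 44 has power 0.802 for a difference of 1.04, so that calculation reproduces and is unaffected. The plan gives no figure for the preference test.

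**Step 1: variance.** With T undecided and T even, the tested count is A + T/2, where A ~ Binomial(n−T, ½) under the null. Its true variance is (n−T)/4; the test assumes n/4. For n = 44 and T = 14 these are 30/4 = 7.5 and 44/4 = 11.

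**Step 2: one result worked through.** Take 21:9 with 14 undecided.
- Sign test: 21 of 30, exact p = 0.0428.
- Split rule: 21 + 7 = 28 of 44, exact p = 0.0961.

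Significance at n = 44 needs 29, that is 22 of the 30 choosers, where the sign test needs 21. True size at T = 14 is therefore 1.6% for the split rule and 4.3% for the sign test.

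At n = 48, 29:15 with 4 undecided moves from p = 0.0488 (29 of 44) to 0.0595 (31 of 48).

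**Step 3: all even counts.** Every even T and every split was enumerated for n = 44 to 48. The split rule never rejects where the sign test does not. The first even T at which the sign test rejects and the split rule does not is 14, 8, 2, 10 and 4 for n = 44, 45, 46, 47 and 48.

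**Step 4: averages over the number undecided.** T ~ Binomial(n, q), stated preferences ~ Binomial(n−T, p), with p = 0.5 for size and 0.75 for power, rejecting when exact p ≤ 0.05. Ranges cover four ways to treat an odd leftover: drop it, assign it at random, give it to the leading lens, or give it to the trailing lens.

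| n | Undecided (q) | Size: split | Size: sign | Power: split | Power: sign |
|---|---|---|---|---|---|
| 44 | 10% | 3.1–4.6% | 3.4% | 87–90% | 88% |
| 44 | 20% | 2.2–3.5% | 3.3% | 78–83% | 83% |
| 44 | 30% | 1.4–2.4% | 3.1% | 65–72% | 76% |
| 44 | 50% | 0.4–0.7% | 2.9% | 29–37% | 59% |
| 48 | 10% | 1.8–2.7% | 3.7% | 85–89% | 91% |
| 48 | 20% | 1.2–1.9% | 3.4% | 75–80% | 87% |
| 48 | 30% | 0.7–1.2% | 3.2% | 60–67% | 81% |
| 48 | 50% | 0.1–0.3% | 3.0% | 22–29% | 64% |

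At n = 44 and 30% undecided, the comparison is 22–27% against 31% for a 65:35 preference, and 96–97% against 98% for 85:15.

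**Step 5: odd counts.** Take 28:15 with 1 undecided at n = 44.
- Leftover to the leader: 29 of 44, p = 0.0488.
- Leftover dropped: 28 of 43, p = 0.0660.
- Leftover to the trailer: 28 of 44, p = 0.0961.

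Always giving it to the leader makes true size at n = 44 equal to 6.6%, 6.0% and 5.3% for T = 1, 3 and 5, and 5.4% at n = 47 with T = 1. Size does not pass 5% this way at n = 45, 46 or 48. Dropping the leftover or assigning it at random keeps size below 5%.

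**The case against.** For even counts the rule errs only on the conservative side, so as written it produces no false claim of preference. The sign test is also conservative (about 3%) and also loses power as more subjects are undecided, from 88% to 59% at n = 44. Only the excess loss belongs to the plan. At n = 44 that excess is about nil at 10% undecided and 0–5 points at 20%, and the largest figures need half the subjects undecided, for which the documents offer no basis. Size above 5% requires a leftover rule that the plan does not suggest; its reasoning points to a neutral one. Keeping everyone in the denominator also describes the whole evaluated group.

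Most of this stands, and it limits the weight of the point. It does not rescue the rule. The p-value is still computed from a wrong variance. At n = 48 the excess loss is already 2–6 points at 10% undecided. The odd-count gap does not depend on any assumed undecided share. Describing everyone needs a table, not an inflated test sample.

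Reading the text as random allocation of each undecided answer would restore calibration (size 4.9% at n = 44). But the result would then depend on chance assignment, and power at n = 48 with 50% undecided would be 33% against 64%. The wording does not read that way in any case.

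**Conclusion.** The concern holds. The even split gives the binomial test the wrong null variance. For even counts the error is conservative: it can only lose detections relative to a sign test. For odd counts the rule is undefined, and one possible completion exceeds 5% size at a few small undecided counts.

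Under the assumptions above, the power cost at n = 44 runs from negligible at 10% undecided to 22–31 points at 50%. The actual cost here is unknown because the plan gives neither the undecided share nor the expected split. Preference is not a listed primary outcome and does not drive the sample size, so this should be corrected but does not threaten the study's main results.

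**What to change.** In Section 11.1, replace the even-split sentence with an exact two-sided binomial (sign) test on subjects who state a preference, at a stated significance level. Beside it, for Visits 4 and 5, report the number and percentage with no preference and the three-category distribution over all evaluated subjects. Say which of the two visits carries the main preference test. Clarify that, for preference, using all evaluated subjects means that all are described and only stated preferences are tested. If the split is kept at all, use it as a descriptive or sensitivity result with a pre-specified rule for an odd count.

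This replaces one sentence, clarifies another and needs no new data. The price is a smaller tested sample and a tested share that describes choosers only, which is why the three-category table must accompany it. The odd-count problem disappears from the main test.

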3.1 Study Hypothesis

- Null hypothesis (Ho): There is no difference in lens performance between Enfilcon A toric and Fanfilcon A toric lenses for the key variables measured.
- Alternative hypothesis (H1): There is a difference in lens performance between Enfilcon A toric and Fanfilcon A toric lenses for the key variables measured.

4 Study Design

This is a prospective, multi-center, subject-masked, bilateral wear, two month dispensing study comparing the clinical performance of the Fanfilcon A toric lenses following a refit and adaptation with Enfilcon A toric lenses (Table 1). The subjects will be fit bilaterally into the Enfilcon A toric lenses at the first visit (or continue wearing their habitual Enfilcon A toric lenses) which will be worn for a minimum of one month and then subjects will be re-fit bilaterally with a pair of Fanfilcon A toric lenses for another month of daily wear. After the dispensing Fanfilcon A toric lens, subjects will return for follow up evaluations after 2 weeks, and 1 month.

The subjects will be advised that they may be dispensed with either Enfilcon A toric lenses OR Fanfilcon A toric lenses, however all subjects will be refit with Fanfilcon A toric lenses. The participant will not be informed on which study lens he/she is wearing during the second month but the investigator will have this information.

5 Study Population

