7.4 Informed Consent

Informed consent (App 18) shall be obtained in writing from the subject and the process shall be documented before any procedure specific to the clinical investigation is carried out.

8 Potential Risks and Benefits to Human Subjects

There may be direct benefits to the subjects in this study, such as improved vision and/or comfort. Participation in a study may contribute to scientific research information that may be used in the development of new contact lens products. In addition, subjects will receive an examination of the front part of their eyes and may have the opportunity to try a different type of soft contact lenses and/or different lens care products at no cost to them. The contact lens materials used in this study are commercially available as daily wear. This study will investigate subjects' wearing schedule intended for daily wear (NOT extended wear), similar to the average wearing time of 10-16 hours for daily wear lenses.

This study is considered to be a non-significant risk study based on United States Food and Drug Administration (FDA) and International Standards Organization (ISO) guidelines, because the study devices used as intended in this study (1) do not represent a potential for serious risk to the health, EX-MKTG-67 v.3.0 Performance of Avaira Vitality Toric Lenses after at least One Month wearing Avaira Toric Lenses (Lavender) 13sep2016

safety or welfare of the subject, and (2) are not implants, (3) are not used to support or sustain human life, (4) are not of substantial importance in diagnosing, curing, mitigating or treating disease or otherwise prevents impairment of human health.

Complications that may occur during the wearing of contact lenses include discomfort, dryness, aching or itching eyes, excessive tearing, discharge, hyperemia and variable or blurred vision. More serious risks may include pain, photophobia, iritis, corneal edema or eye infection. Although contact lens-related infections are very infrequent, the possibility does exist. The incidence of infection due to day-wear soft lenses is 0.035%. Almost always an infection will occur only in one eye. This risk is assumed by 35-million Americans who currently wear contact lenses and only current soft lens wearers will be recruited for this study.

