- For a subject who is a current Avaira Toric wearer but requires a change in prescription, please complete Avaira Toric Prescription Form (App 2B) and schedule Visit 2.
- For a subject who is not a current Avaira Toric wearer, please complete Trial Lens Fitting Form (App 2A) and fit lenses accordingly, after the trial lens fit was successful, complete Avaira Toric Prescription Form (App 2B) and schedule Visit 2.

- Anterior segment ocular health will be assessment (App 4)
 - External Adnexa anomalies (Present/Absent & Describe)
 - Hyperemia
 - Bulbar (0-4, 0.5 steps)
 - Limbal (0-4, 0.5 steps)
 - Palpebral (0-4, 0.5 steps)
 - Cornea & Anterior eye
 - Infiltrates (0- 4, 1 step)
 - Conjunctival infection (0-4, 1 step)
 - EKC (0-4, 1 step)
 - Corneal ulcers (0-4, 1 step)
 - Lens Adhesions (0-4, 1 step)
 - Recurrent Erosions (0-4, 1 step)
 - Other abnormalities (0-4, 1 step)
 - Staining
 - Corneal Staining (0-4, 0.5 step & Optional sketch of staining)
 - Conjunctival Staining (0-4, 0.5 step)
 - Conjunctival Indentation (0-4, 0.5 step)
 - Other findings
- Eligibility Checklist (App 5) will be completed
- Complete Enrolment Log (App 20). If at this point the subject is found to be ineligible, then complete an Exit form (App 13) and exit the subject from the study.

- If a subject is a current Avaira Toric lens wearer and no change to the lens prescription is required then the subject will be instructed to wear the lenses on a daily wear basis, (at least 5 days/week, >8 hours/day), until Visit 3 appointment can be scheduled, unless they experience a problem which warrants lens removal.
- If a subject requires a new prescription for Avaira Toric lenses, please complete the Avaira Toric Prescription Form (App 2B), order the lenses and schedule Visit 2
- If a subject is not a habitual Avaira Toric wearer, re-fit subject into Avaira Toric lens using the Trial Lens Fitting Form (App 2A). After the fit was successful, please complete the Avaira Toric Prescription Form (App 2B), order the lenses and schedule Visit 2.

In some circumstances a repeated Screening may need to be scheduled. Examples include, but are not limited to:

1. Study procedures unable to be completed in time scheduled for visit;
2. Study products not available at the time of the study visit;
3. A transient health condition which may affect the eye(s) (e.g. a common cold, active allergies, fatigue etc.);
4. The short term use of medications (e.g. antibiotics, antihistamines etc.);

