 - Remove study lenses and perform slit lamp assessment to establish anterior segment ocular health.
 - Monocular high contrast visual acuity with sphero-cylindrical refraction (Snellen)
 - If the VA at the Exit Visit is two or more lines worse than at Screening, repeat a monocular sphero-cylindrical refraction (sphere, cylinder and axis) if the best corrected spectacle vision remains two or more lines worse than at Screening, the Investigator will be required to provide an explanation and complete an adverse event form if needed.
 - Post-study follow-up requirement (Y/N). If yes, the reason and date of the follow-visit must also be recorded.
- If the subject is being exited due to discontinuation, further details need to be recorded on the Study Exit Form (App 13).

10 Adverse Events and their Reporting

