10.2 Procedures for Adverse Events

Treatment of an adverse event will depend on its nature and severity. Based on the clinical judgment of the investigator the subject may be referred to an ophthalmologist for treatment. The investigator will attempt to determine whether the reaction is related to the study device/procedure or a result of other factors.

An Adverse Event Form will be completed for each adverse event. If both eyes are involved, a separate Adverse Event Form will be completed for each eye. Whenever possible, the adverse event will be photo-documented.

Expenses incurred for medical treatment as part of study participation will be paid by the sponsor (bills and prescription receipts kept). The subject must be followed until resolution and a written report completed indicating the subsequent treatment and resolution of the condition.

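### Section 11.1 plans no subject-level counts of slit-lamp worsening or adverse events by lens, and its default of mean grades at matched visits can show no difference when a few subjects have new corneal findings

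*Combined protocol and SAP*

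**What the plan says.** Table 2 (Study Forms) marks biomicroscopy at all five visits. Section 9.3.1 lists what is graded: hyperemia and staining on 0-4 scales in half steps; infiltrates, conjunctival infection, ulcers and similar findings on 0-4 scales in whole steps. Visit 5b (Study Exit) adds, among the measurements at the final visit: "Remove study lenses and perform slit lamp assessment to establish anterior segment ocular health".

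Section 11.1 is the only analysis section and shows no redaction. It names neither slit-lamp grades nor adverse events. Its general provisions are:

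- "Means and standard deviations will be provided for each variable".
- Paired t-tests for differences between lenses and over time, or ANOVA, for normal data, with the test chosen after normality testing. No alternative test is named.
- A binomial test, for preference counts alone.
- All evaluated subjects are used, and "In the event of missing data, individual data points will be excluded in the analysis and not extrapolated from the collected data".

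Section 10.1 classes and codes adverse events. On forms, section 10.2 says: "If both eyes are involved, a separate Adverse Event Form will be completed for each eye". Section 8 says of infection: "Almost always an infection will occur only in one eye".

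**The concern.** The study asks whether wearers of the control lens can be confidently refit into the test lens and succeed with it. For ocular health that is a question about how many subjects develop a new finding, and a mean grade answers it poorly, for two reasons.

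1. Grades for infiltrates, ulcers and infection should be zero in nearly everyone and, for infection, usually raised in one eye. A mean over subjects, and more so over eyes, dilutes a few real findings. Small improvements in many subjects can also offset large worsening in a few.
2. A paired Visit 3 to Visit 5 comparison needs a Visit 5 value. A subject who leaves earlier, for whatever reason, contributes nothing to it.

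Without a planned count and denominator, the report could describe ocular health as unchanged on mean grades while the adverse-event forms hold findings that were never expressed as a rate by lens.

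**Working it through.** **The plan's own figure.** Section 5.1 takes SD 2.4 (comfort before removal, 0-10 scale), "For an alpha level of 0.05 and power of 0.8", n = 44 and a detectable difference of 1.04. The alternative in section 3.1 is non-directional, so I use a two-sided test.

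- Normal approximation for paired data: n = (SD × (z0.975 + z0.80) / difference)² = (2.4 × 2.8016 / 1.04)² = 41.8, so 42.
- Noncentral t: power is 0.802 at n = 44 and 0.793 at n = 43; the detectable difference at n = 44 is 1.037.

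The stated 44 reproduces if 2.4 is the SD of the paired difference. It is sized on comfort and gives no assurance about slit-lamp findings.

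**Allowed loss.** 48 dispensed − 44 analysed = 4, and 4/48 = 8.3%.

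**Dilution.** Suppose k of n subjects rise by g grades and the rest do not change. The mean change is kg/n. The variance is kg²(n − k) / (n(n − 1)), so t = √(k(n − 1)/(n − k)), in which g cancels. At n = 44 (43 df):

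| k | t | p | mean if g = 2 | mean if g = 3 |
|---|---|---|---|---|
| 1 | 1.00 | 0.32 | 0.05 | 0.07 |
| 2 | 1.43 | 0.16 | 0.09 | 0.14 |
| 3 | 1.77 | 0.083 | 0.14 | 0.20 |
| 4 | 2.07 | 0.044 | 0.18 | 0.27 |

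With no other variation, three new findings of any common grade miss p < 0.05. If each is in one eye and eyes are averaged, the k = 3, g = 2 mean halves to 0.07 and p is unchanged. As a count, 3/44 = 6.8%, exact (Clopper-Pearson) 95% CI 1.4% to 18.7%.

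With an assumed background SD of 0.3 to 0.7 grade in the paired difference (the documents give none), simulation of a 3-grade rise gives p < 0.05 in 6-9% of trials for k = 2, 16-18% for k = 3 and 27-42% for k = 4.

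**Cancellation.** This staining example is built to cancel: 20 subjects at −0.5, 19 at 0, 5 at +2. The sum is −10 + 0 + 10 = 0, so the mean is 0 and p = 1.0. Yet 5/44 = 11.4% (3.8% to 24.6%) worsened by two grades.

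**Would a rank test help?** A signed-rank test (zeros dropped, normal approximation) gives p = 0.083 for three infiltrates. For the staining case p = 0.17, and the rank sums favour improvement: 20 × 10.5 = 210 negative against 5 × 23 = 115 positive. A non-parametric choice after normality testing would not close the gap.

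**Early exit.** Suppose all four allowed losses have an event and leave before Visit 5. The Visit 3 to Visit 5 comparison then holds 44 subjects and no events; the exact 95% upper limit is 1 − 0.025^(1/44) = 8.0%, which a mean of 0.00 would not convey. Over all dispensed, 4/48 = 8.3% (2.3% to 20.0%).

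All event counts here are assumptions.

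**The case against.** Much of the case on the other side stands.

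- **Section 11.1 never says slit-lamp grades will be analysed this way.** True; it follows from wording about each variable. A reader might infer that only paired t-tests apply, but the text allows ANOVA and a choice guided by normality tests. It names no method for ordinal, zero-heavy grades. If 11.1 is instead read as silent on slit-lamp data, no safety analysis is specified, and the remedy is the same.
- **Corneal events are not lost to the study.** A reader might infer that they are. But section 10.1 has codes for ulcers, symptomatic and asymptomatic infiltrates, moderate or worse staining and conjunctivitis. Sections 10.2 to 10.4 require a form per event, reporting to the sponsor and follow-up to resolution, and section 12.1 has adverse-event cases discussed before export. This is capture and reporting; it sets no denominator or rate by lens.
- **Leaving early does not remove a subject from every comparison.** Someone seen at Visit 4 still has a Visit 3 to Visit 4 pair, and excluding missing points without extrapolating is not a fault.
- **Slit-lamp readings for early leavers are not guaranteed.** The exit examination is listed for the final study visit, discontinued subjects need further details on a form we cannot see, and section 13 makes unscheduled-visit data optional.
- **The illustrations are not forecasts.** The infection incidence in section 8, 0.035%, gives 48 × 0.00035 = 0.02 expected cases.
- **Redactions** in the synopsis, the visit procedures and section 10.3 mean that a safety endpoint or summary may exist out of sight.

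**Conclusion.** The point holds as a modest gap in the analysis plan. Under its general rule, 11.1 would summarise ordinal slit-lamp grades by means, and the visible text plans no adverse-event incidence by lens. At n = 44, new findings of a common grade in up to three subjects (6.8%) would not reach p < 0.05 on mean grades even with no other variation. Up to four events among 48 dispensed (8.3%) could fall outside the Visit 3 to Visit 5 comparison.

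This rests on three assumptions: that the general rule is applied to slit-lamp grades, that the event counts are as illustrated, and that redacted text holds no safety summary. A reader might go further and call the lens comparison biased toward safety. The documents do not support that: they give no evidence that losses will be caused by corneal events, and such events would be recorded elsewhere.

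**What to change.** Add a safety paragraph to 11.1:

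1. **Adverse events.** Number and percent of subjects (not forms, since a bilateral event produces two), by class and by lens worn at onset, over all subjects dispensed that lens, with exact 95% CIs.
2. **Slit-lamp grades.** For each variable, using the worse eye:
   - a shift table from Visit 3a to Visit 5, or to the last available post-dispense reading;
   - the number and percent of subjects whose worst available post-dispense grade (Visit 4, Visit 5, and exit or unscheduled readings where recorded) rose from Visit 3a by at least a prespecified analysis threshold larger than one scale step, with exact 95% CI.

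Keep means as secondary summaries if wanted. The sponsor should set the threshold before data export; it is for analysis and carries no rule for managing subjects.

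The cost is a few lines and two or three tables from forms already in use, with no change to sample size or visits. The downside is that the worst of several readings against a single Visit 3a reading overstates worsening: with two exchangeable post-dispense readings and no ties, noise alone makes 2/3 of subjects look worse, against 1/2 with one. The threshold and the Visit 5 shift table limit this. The slit-lamp count has no control-lens equivalent, so it should be labelled descriptive.
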